#### 4. SUBJECT REGISTRATION

All subjects must be registered through HCRN electronic data capture (EDC) system. A subject is considered registered when an "On Study" date is entered into the EDC system.

Subjects must be registered and randomized prior to starting protocol therapy. Subjects must be randomized within one business day of registration and begin therapy within 5 business days of randomization.

#### 4.1 Blinding

Site pharmacy staff and HCRN EDC administrative team will be unblinded to the study treatment. Subjects, site investigators, site analysis teams, and other site personnel will be blinded to the study treatment.

Unblinding of site personnel may occur for emergency purposes only. Site investigators should note that the occurrence of a serious adverse event or progressive disease should not routinely precipitate the immediate unblinding of the label. The site investigator will contact HCRN to unblind a subject. If this is not feasible, HCRN must be notified **within 24 hours** of unblinding.

In compliance with applicable regulations, in the event of a serious adverse event (SAE), the subject's treatment assignment may be unblinded before reporting to the health authorities, ethic committees, and site investigators if the SAE was related (possibly, probably, definitely) to the blinded treatment.

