**Evaluation of non-target lesions** 

Complete Response (CR)	Disappearance of all non-target lesions and normalization of tumor marker level. All lymph nodes must be non-pathological in size (<10 mm short axis)
	Note: If tumor markers are initially above the upper normal limit, they must normalize for a subject to be considered in complete clinical response.
Non-CR/ Non-PD	Persistence of one or more non-target lesion(s) and/or maintenance of tumor marker level above the normal limits
Progressive Disease (PD)	Appearance of one or more new lesions and/or unequivocal progression of existing non-target lesions. Unequivocal progression should not normally trump target lesion status. It must be representative of overall disease status change, not a single lesion increase.

Although a clear progression of "non-target" lesions only is exceptional, the opinion of the treating physician should prevail in such circumstances, and the progression status should be confirmed at a later time by the sponsor-investigator.

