## 10.2.2.3 Sponsor-Investigator Responsibilities

HCRN will send a SAE summary to the sponsor-investigator **within 24 hours** of receipt of SAE Submission Form from a site. The sponsor-investigator will promptly review the SAE summary and assess for expectedness and relatedness.

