# 10.2.2.4 HCRN Requirements for Reporting to the Food and Drug Administration (FDA)

This protocol was determined to be exempt from the requirements of an IND by the FDA. HCRN will continue to facilitate compliance of applicable requirements for the sponsor-investigator in relation to this study. This includes but is not limited to 21 CFR 50.20 informed consent, 21 CFR Part 56 IRB, and pertinent sections of the Public Health Service Act and FDAAA.

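### Section 4.1 limits site unblinding to emergencies, then permits unblinding before related-SAE reports go to site investigators, with nothing keeping the sites' copy blinded

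*Combined protocol and SAP*

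**What the plan says.** Section 4.1 (Blinding) sets out three things.

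- **Roles.** "Subjects, site investigators, site analysis teams, and other site personnel will be blinded to the study treatment". By contrast, "Site pharmacy staff and HCRN EDC administrative team will be unblinded to the study treatment".
- **Limit.** "Unblinding of site personnel may occur for emergency purposes only". Site investigators are also reminded that the "occurrence of a serious adverse event or progressive disease should not routinely precipitate the immediate unblinding of the label".
- **Related SAEs.** The last paragraph, introduced as compliance with applicable regulations, states that "the subject's treatment assignment may be unblinded before reporting to the health authorities, ethic committees, and site investigators if the SAE was related". Related here means possibly, probably or definitely related to the blinded treatment.

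Section 11.8 (Un-blinding Plan) only refers back to 4.1.

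On the endpoint, sections 8.3.7 and 11.2 define PFS by RECIST 1.1 progression or death. Section 7.1.6 has the sites continue tumor evaluation every 8 weeks after treatment stops without documented progression. For progression in non-target lesions alone, section 8.2 gives precedence to the treating physician's view and adds that "the progression status should be confirmed at a later time by the sponsor-investigator".

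**The concern.** The second and third paragraphs of 4.1 give different rules for the same people. One allows a site to be unblinded only in an emergency. The other permits unblinding ahead of a report whose recipients include site investigators, on relatedness alone.

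The condition is not narrow. Section 10.1.4 defines a possible relation as one that may exist, and section 10.1.2 makes any event needing inpatient admission serious.

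At stake is the blind on PFS. An assessor who knows the arm could be influenced in calling non-target progression. Under section 7.1.6 the site investigator also judges when off-treatment scans are no longer feasible, and section 8.3.7 censors subjects without progression at their last disease evaluation. Knowledge of the arm could thus reach both event calls and censoring. The trial is described as double-blind throughout, and its one-sided type I error is already 0.20.

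**Working it through.** **1. The two rules in 4.1, side by side**

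| | Second paragraph | Last paragraph |
|---|---|---|
| Trigger | Emergency | SAE at least possibly related to the blinded treatment |
| SAE as a routine trigger | Discouraged | Relatedness is sufficient |
| Emergency required | Yes | No |
| Unexpected event required | Not addressed | No |
| Site investigators | Unblinded only in an emergency | Named among the report recipients |
| Blinded copy for sites | Not applicable | Not required |

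**2. Does another section close the gap?** Section 11.8 adds nothing. Section 12.1 has HCRN notify participating sites of expedited events and does not say that the notices omit the assignment. Section 10.2.2 covers SAE reporting to HCRN, the manufacturer and the sponsor-investigator, and does not mention the assignment.

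**3. Does the gap reach the primary endpoint?** Sites evaluate tumors (study calendar footnote 9; section 7.1.6). No central or independent reader is named. The sponsor-investigator confirms non-target-only progression (section 8.2), but 4.1 places that role in neither the blinded nor the unblinded list.

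**4. Design figures (section 11.10), reproduced as background**

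Inputs: medians 6 and 9 months, one-sided alpha 0.20, power 80%, accrual 24 months, follow-up 9 months.

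- Events (Schoenfeld): 4 × (0.8416 + 0.8416)² / (ln 1.5)² = 68.9, so 69.
- Event probability: 1 − [exp(−9λ) − exp(−33λ)] / (24λ), with λ = ln 2 / median. This gives 0.880 (control) and 0.772 (ramucirumab).
- Expected events: 43 × 0.880 + 42 × 0.772 = about 70.3.
- Power: Φ(½ × √70.3 × ln 1.5 − 0.8416) = 0.805, against 0.8014 stated.

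The design is one-sided at 0.20 and is not in dispute.

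**5. Illustration of sensitivity (assumed inputs)**

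Null trials were simulated with exponential PFS, median 6 months in both arms, 43 and 42 subjects, 24 months' accrual and 9 months' follow-up. Scans were 8-weekly and the log-rank test was one-sided at 0.20. Progression was then called one scan late in an assumed share of the ramucirumab arm only. Ranges cover set-ups with all or 80% of events found on scans and, where stated, 2,000 to 4,000 trials per setting. The Monte Carlo standard error is √(0.2 × 0.8 / 2,000) = 0.009 at most runs' smallest size, and 0.006 at 4,000.

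| Share deferred | Subjects of 42 | Rejection rate |
|---|---|---|
| 0% | 0 | 0.19–0.21 |
| 10% | 4.2 | 0.22–0.23 |
| 20% | 8.4 | 0.25–0.28 |
| 40% | 16.8 | 0.29–0.33 |

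The 10% row is hard to separate from no effect. The shares, the single direction and the one-scan delay are all assumptions.

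**6. Would excluding unblinded subjects help?**

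Suppose there is no assessor bias and no treatment effect (λ = ln 2 / 6 = 0.1155 per month), with assumed unblinding rates of 0.03 (ramucirumab) and 0.015 (control) per month. Ignoring administrative censoring:

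- Share excluded: 0.03 / (0.03 + 0.1155) = 21% and 0.015 / (0.015 + 0.1155) = 11%.
- Progression times among those retained have rates 0.1455 and 0.1305, an artificial hazard ratio of 1.11 against ramucirumab.
- With rates 0.05 and 0.02, the ratio is 0.1655 / 0.1355 = 1.22.

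In simulation the nominal 0.20 test then rejected in about 10 to 12% and 6 to 7% of trials respectively. The exclusion creates a bias of its own.

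**The case against.** The strongest defence is that the last paragraph says less than it first appears to. It is permissive. It speaks of unblinding before reporting, not of telling the site. HCRN staff who already hold the assignment could do the unblinding. An SAE attributed only to the open-label chemotherapy does not qualify. Most progression is also measured: section 8.2 requires a 20% and 5 mm increase in target lesions, and it calls clear non-target-only progression exceptional.

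All of this stands, and it rules out several stronger readings that a reader might infer:

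- **That sites will be told the assignment.** The text permits this and does not say it.
- **That sites are the only assessors.** Section 8.2 adds confirmation by the sponsor-investigator for non-target-only progression.
- **That the sponsor-investigator is unblinded.** Section 10.2.2.3 says "The sponsor-investigator will promptly review the SAE summary and assess for expectedness and relatedness". Nothing shows that the summary carries the assignment, and absence from the blinded list is not evidence of unblinding.
- **That symptomatic deterioration or a change of therapy is a biased PFS event.** Neither is an event under section 8.3.7, and scans continue afterwards where feasible.
- **That unblinding would be more frequent on ramucirumab.** This is plausible, but the documents give no rate.

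The appeal to applicable regulations does not settle the matter either way. The paragraph names no rule that requires site investigators to receive an unblinded report. Section 10.2.2.4 records that "This protocol was determined to be exempt from the requirements of an IND by the FDA", which alone does not prove that no rule applies.

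What the defence does not answer is that 4.1 names site investigators as recipients and nothing keeps their copy blinded.

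**Conclusion.** Section 4.1 contradicts itself on when a site investigator may learn the assignment, and no other section resolves it. Because sites evaluate progression and no independent reader is named, the plan as written permits unblinded assessment of the primary endpoint. It does not show that this will occur.

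The size of any effect is unknown. A reader might take the simulated rejection rates as the trial's real type I error, but the documents do not support that. They give no SAE or unblinding rate and no link from unblinding to a deferred call. The figures show only that a one-sided consequence in about a fifth or more of the ramucirumab arm would be visible at this sample size.

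The point should be corrected because it touches the blind on PFS and costs almost nothing to close. It is not a reason to question the design or the sample size.

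**What to change.** - **Section 4.1, last paragraph.** Remove site investigators from the recipients, or state that SAE reports and notices to sites stay blinded. Any unblinded version would be prepared by the already unblinded HCRN staff, for health authorities and ethics committees only. Apply the same wording to the site notices in section 12.1.
- **Emergency unblinding.** Leave it unchanged.
- **Sponsor-investigator.** State in 4.1 that this role is blinded, since it confirms non-target-only progression.
- **Reporting.** Tabulate the number and timing of unblindings by arm.
- **Analysis.** Keep the ITT log-rank test as primary. Do not add an analysis excluding subjects unblinded before progression: it conditions on a post-randomization event and departs from the principle in section 11.9.

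The cost is a short amendment and one table, with no extra reader or visit. The downside is that sites receive blinded SAE notices unless emergency unblinding is requested.

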#### 5. TREATMENT PLAN

#### 5.1 Treatment Regimen

One cycle will be equal to 28 days. The ramucirumab/placebo will be administered prior to the mFOLFIRINOX regimen. Both arms will receive mFOLFIRINOX regimen given per institutional standards (suggested administration sequence below), which will be a modification of the previously published regimen.  mFOLFIRINOX will be administered every 2 weeks. Dose modifications for all medications are outlined in Section 6:

- Arm A will receive ramucirumab administered as an intravenous infusion over 60 minutes (infusion rate should not exceed 25 mg/min), at a fixed dose of 8 mg/kg every 2 weeks.
- Arm B will receive a placebo infusion. Due to the double-blinded nature of this study, the volume of placebo will be calculated as if it were ramucirumab.
- Oxaliplatin 85 mg/m^2 over 2-4 hours
- Irinotecan 165 mg/m^2 over 90 minutes
- 5-FU 2,400 mg/m^2 as a 46-hour continuous infusion without the 5-FU bolus to decrease the risk of neutropenia.

Leucovorin is not included in this regimen since the 5-FU is administered as a continuous infusion and not in bolus form.

Version Date: 13AUG2018 Confidential Page 15 of 51

#### 5.2 Pre-medications and Home Medications

#### **5.2.1** Pre-medications

The following medications will be administered:

- Palonosetron 250 mcg IV within 30 minutes prior to oxaliplatin and 5-FU
- Dexamethasone 20 mg IV or PO within 30 minutes prior to oxaliplatin and 5-FU
- Atropine 0.4 mg IV within 30 minutes prior to Irinotecan. May repeat 1 dose for cramping or diarrhea.
- Diphenhydramine 50 mg IV within 30 minutes prior to ramucirumab/placebo.

#### **5.2.2** Home Medications

The following are suggested medications to be provided to the subject to take home:

- Prochlorperazine 10 mg PO every 6 hours PRN nausea/vomiting.
- Loperamide PRN diarrhea. Subject will be instructed to take 4 mg PO at onset of diarrhea, followed by 2 mg PO every 2 hours (or 4 mg every 4 hours at night) until 12 hours have passed without a bowel movement.

# 5.3 Drug Administration

**Table 2. Drug Administration** 

Drug	Dose	Frequency of administration	Route of administration
Ramucirumab or Placebo	8 mg/kg	Every 2 weeks	IV; infusion rate should not exceed 25 mg/min
Oxaliplatin	85 mg/m 	Every 2 weeks	IV over 2 to 4 hrs
Irinotecan	165 mg/m 	Every 2 weeks	IV over 90 min
5-FU	2,400 mg/m 	Every 2 weeks	IV 46-hour continuous infusion

Body surface area and drug doses should be recalculated for subject's whose weight changes by  $\geq$  10% during the course of the study.

Leucovorin is not included in this regimen since the 5-FU is administered as a continuous infusion and not in bolus form.

#### 5.3.1 Missed Doses

All medications are given on Day 1. A missed dose implies delay of that cycle. Infusions may be given within 3 days for reasons such as observed holidays, inclement weather, scheduling conflicts, etc. It should be clearly documented in subject's chart and case report forms

Version Date: 13AUG2018 Confidential Page 16 of 51

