# STATISTICAL CONSIDERATIONS

We aim to test the null hypothesis of PFS at 6 months. Using a one-sided log-rank test we have estimated a sample size of 85 patients (43 in one and 42 in another arm) which will provide 80% power under a type 1 error of 20%. This is an estimation on 24 months accrual and 9 months follow up after accrual for the primary endpoint. Sample size may increase to 95 to account for a 10% drop out rate.

The primary endpoint of this clinical trial is PFS. PFS is defined as the time from enrollment to the time of progression or death. An interim analysis with Kaplan Meier method and Logrank test will be conducted after 23 subjects have been enrolled in each arm and followed up for 9 months. The trial will stop if it detects a significant difference of 3 months in PFS between the study arm-mFOLFIRINOX/RAM, as compared to the standard arm-mFOLFIRINOX at the significance level of 0.0013 according to the O'Brien-Fleming approach. Otherwise the trial will continue until the targeted sample size has been completed.

RR, PFS and OS will be reported with 95% confidence intervals. Response is defined as a complete or partial response according to CT/MRI evaluations based on RECIST 1.1 criteria. Toxicity will be graded using CTCAE v4

**Early stopping:** In the case of excessive toxicity, safety-stopping rules will be used. A grade  $\geq 3$  or adverse event that will lead to stop or termination of treatment is defined as suspected treatment related toxicity observed in the first 4 weeks of enrollment after dose modification, but excluding: nausea or vomiting and hematologic toxicities if not adequately treated. Ramucirumab will be held for drug related adverse events grade  $\geq 3$  until recovery to grade  $\leq 1$  and then resumed with a lower dose level -1 (6 mg/kg). If the grade  $\geq 3$  related adverse events does not resolve within 3 weeks of holding treatment, subject will be taken off the trial. In the case of prolonged or medically concerning grade 2 toxicity related to chemotherapy combination, treatment will be interrupted until

[figure not shown]

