# 6.1 Dose Modifications for Ramucirumab/placebo

Ramucirumab/placebo will be held for Grade  $\geq 3$  study drug related adverse events until recovery to Grade  $\leq 1$  and then resume with a dose reduction (level -1; 6 mg/kg) if site investigator evaluation relates toxicity to ramucirumab/placebo. If a second Grade  $\geq 3$  drug related adverse event is experienced and does not resolve within 2 weeks of the initial dose reduction, an additional dose reduction (level -2; 5mg/kg) will be made. If Grade  $\geq 3$  related adverse event does not resolve within 2 weeks of the second dose reduction, the subject will be taken off the trial.

Table 3. Modified dose of ramucirumab

Dose level	Ramucirumab
Starting dose	8 mg/kg
Level -1 dose reduction	6 mg/kg
Level -2 dose reduction	5 mg/kg

Version Date: 13AUG2018 Confidential Page 20 of 51

Table 4. Dosing level of ramucirumab/placebo for treatment related adverse events

Toxicity NCI	Worst Interval Toxicity	Day of Treatment
Grade (value)		
1	Maintain dose level	Continue treatment per protocol schedule.
2	Maintain dose level	Hold until resolved to grade 1 or less.
3	Reduce to dose level -1 6 mg/kg	Hold until resolved to grade 1 or less.
4	Reduce to dose level -2 5 mg/kg	Hold until resolved to grade 1 or less.

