#### **6.1.1** Management of Hypertension

Interrupt ramucirumab/placebo for severe hypertension until controlled with medical management. Permanently discontinue ramucirumab/placebo for severe hypertension that cannot be controlled with antihypertensive therapy. The subject will continue to be followed per guidelines in Section 7. Subjects with grade 4 hypertension must not receive further treatment with ramucirumab

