#### 6.1.2 Proteinuria

Interrupt ramucirumab/placebo for urine protein levels  $\geq 2$  g/24 hours. Reinitiate treatment at a dose level -1 reduction (see Table 3) once the urine protein level returns to <2 g/24 hours. If the protein level  $\geq 2$  g/24 hours reoccurs, interrupt ramucirumab/placebo and reduce the dose to dose level -2 (table 4) once the urine protein level returns to <2 g/24 hours. Permanently discontinue ramucirumab if there is a third occurrence of >2 g/24 hours, or if the protein level does not return to <2 g/24 hours within 2 weeks. Permanently discontinue ramucirumab/placebo for urine protein level >3 g/24 hours or in the setting of nephrotic syndrome

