# 6.1.6 Conditions for permanent discontinuation of ramucirumab/placebo

Listed below are clinical conditions in which ramucirumab/placebo should be permanently discontinued.

- Grade 3 and 4 arterial thromboembolic events, or any PE/DVT occurring or
  worsening during anticoagulant therapy. Any arterial event leading to
  discontinuation of ramucirumab therapy will be considered serious and should be
  reported via the serious adverse event (SAE) mechanism.
- Subjects with Grade 4 hypertension must not receive further treatment with ramucirumab
- Gastrointestinal Perforation
- Grade 3 or 4 Bleeding
- Grade 3 or 4 Infusion Reaction
- Hepatic encephalopathy or other serious signs of liver impairment such as hepatorenal syndrome
- Fistula Formation
- Reversible Posterior Leukoencephalopathy (RPLS); All cases of RPLS must be reported via the SAE reporting guidelines.

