## 11.6 Excessive Toxicity – Criteria for Stopping and Interim Safety Analysis

In case of excessive toxicity, safety-stopping rules will be used. An acceptable toxicity rate will be assumed at 0.20. The study will be stopped based on an unacceptable excessive toxicity rate of 0.40. A sequential probability ratio test will be used where a likelihood ratio of 8 in favor of an excessive toxicity rate of 0.40 (vs. 0.20) provides sufficient evidence to stop the study due to excessive toxicity. Data will be continuously reviewed for excessive toxicity and statistical analysis performed if excessive toxicity is suspected. The table below provides the minimum number of patients exhibiting excessive toxicity that will trigger statistical analysis.

Total number of treated patients	Number of Patients observed with excessive toxicity
3	≥2
4-5	≥3
6-7	≥4
8-9	≥5
10-11	≥6
12-13	≥7
14-16	≥8
17-18	≥9
19-20	≥10

Version Date: 13AUG2018 Confidential Page 41 of 51

21-23	≥11
24-25	≥12
26-28	≥13
29-30	≥14
31-33	≥15
34-35	≥16
36-38	≥17
39-40	≥18

Ramucirumab will be held for drug related adverse events Grade  $\geq 3$  until recovery to Grade  $\leq 1$  and then resumed with a lower dose level -1 (6 mg/kg). If the Grade  $\geq 3$  related adverse event does not resolve within 4 weeks of holding treatment, the subject will be taken off study treatment.

In the case of prolonged or medically concerning Grade 2 toxicity related to the chemotherapy combination, treatment will be interrupted until recovery to Grade  $\leq 1$ , at which time treatment will be resumed at the same dose. If the adverse event does not resolve in or within 2 weeks with medical intervention, then the subject will be taken off study treatment.

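### Inconsistent instructions on mFOLFIRINOX, and on the subject's status, when ramucirumab/placebo is held or stopped for toxicity

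*Combined protocol and SAP*

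**What the plan says.** All references are to the combined protocol and SAP.

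- **Schedule.** Section 5.1: "mFOLFIRINOX will be administered every 2 weeks". Ramucirumab/placebo has the same interval, and the study calendar (section 7) gives both on Day 1 and Day 15 of a 28-day cycle.
- **Rules naming ramucirumab/placebo only.** Section 6.1.1: "Interrupt ramucirumab/placebo for severe hypertension until controlled with medical management", with a permanent stop if blood pressure cannot be controlled. Section 6.1.2: "Permanently discontinue ramucirumab/placebo for urine protein level" above a stated threshold, after a hold-and-reduce sequence. Section 6.1.3 interrupts it around surgery. Section 6.1.6: "Listed below are clinical conditions in which ramucirumab/placebo should be permanently discontinued"; its list includes Grade 3 or 4 bleeding and Grade 4 hypertension. None of these mentions mFOLFIRINOX.
- **Rules that reach further.** For a Grade 3 or higher related event, section 11.6 says: "event does not resolve within 4 weeks of holding treatment, the subject will be taken off study treatment". The synopsis (Statistical Considerations, early stopping) says: "related adverse events does not resolve within 3 weeks of holding treatment, subject will be taken off the trial". Section 6.1 says: "related adverse event does not resolve within 2 weeks of the second dose reduction, the subject will be taken off the trial".
- **General rules.** Section 5.3.1: "All medications are given on Day 1. A missed dose implies delay of that cycle". Section 6.3 ends protocol therapy after an interruption of 30 days or more.

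**The concern.** The primary objective compares mFOLFIRINOX plus ramucirumab with mFOLFIRINOX plus placebo. Reading the result as what ramucirumab adds requires the backbone to be delivered under the same rules whatever happens to the blinded drug. The text leaves two routes by which toxicity of the blinded drug can reach the backbone: a delay of the whole cycle (5.3.1, read literally) and removal from treatment or trial (synopsis, 6.1, 11.6). Sections 6.1.1 to 6.1.6 suggest neither.

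The triggers may fall unevenly. Section 9.1.5 lists hypertension and proteinuria for ramucirumab. The lists for 5-FU, irinotecan and oxaliplatin (9.2.2, 9.3.3, 9.4.4) contain neither. Bleeding is weaker evidence, because 5-FU and irinotecan list it too. If sites resolve the ambiguity differently, a null PFS result could partly reflect lost chemotherapy, and section 11 plans no dose-intensity summary that would show it.

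The subject's status matters as well. Sections 6.3 and 7.1.6 continue follow-up after therapy stops, and section 6.4 treats leaving the study as something separate. Off study treatment and off the trial are therefore not interchangeable.

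**Working it through.** **1. The plan's own figure.** Inputs from section 11.10: medians 6 and 9 months (HR 6/9 = 0.6667), one-sided alpha 0.20, power 0.80, 24 months accrual plus 9 months follow-up, 43 + 42 subjects.

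- Schoenfeld events: 4(0.8416 + 0.8416)² / (ln 0.6667)² = 11.33 / 0.1644 = 68.9, so 69. Freedman: 2.833 × (1.6667/0.3333)² = 70.8, so 71.
- Event probabilities (exponential PFS, uniform accrual): 0.880 control, 0.772 treatment, mean 0.826. N = 69/0.826, rounded up to 84, or 71/0.826, rounded up to 86, against 85 stated.
- With 43 + 42 subjects, 43 × 0.880 + 42 × 0.772 = 70.3 events and power 0.805, against 0.8014 stated.

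The sample size reproduces and is not in question.

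**2. One event under each section.** Take Grade 3 bleeding judged related to ramucirumab/placebo.

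| Section | Ramucirumab/placebo | Limit | Status if unresolved |
|---|---|---|---|
| 6.1.6 | permanent stop | none | not stated |
| 6.1 text | hold, resume at level -1; later level -2 | 2 weeks after second reduction | off the trial |
| Synopsis | hold, resume at level -1 | 3 weeks of holding | off the trial |
| 11.6 | hold, resume at level -1 | 4 weeks of holding | off study treatment |

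Section 11.6.1 lists ramucirumab, oxaliplatin, irinotecan and 5-FU as the study treatments, so the last row plausibly ends the backbone. No row says what happens to mFOLFIRINOX during the hold, or after a permanent stop under 6.1.6.

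Grade 4 hypertension shows the same split. Sections 6.1.1 and 6.1.6 bar further ramucirumab. If the event is related, Table 4 allows a return at level -2 after recovery, while the text of 6.1, the synopsis and 11.6 allow one at level -1.

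Section 6.2 does not fill the gap. Its adjustments depend on toxicity attributed to the chemotherapy drugs. It does modify oxaliplatin alone for neurologic toxicity, so handling by component exists in the protocol.

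**3. The 30-day rule.** With a dose due every 14 days:

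| Hold | Days from missed dose | Days from last dose |
|---|---|---|
| 2 weeks | 14 | 14 + 14 = 28 |
| 3 weeks | 21 | 14 + 21 = 35 |
| 4 weeks | 28 | 14 + 28 = 42 |

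Counted from the missed dose, no hold reaches 30 days. Counted from the last dose, the 3- and 4-week holds do. Section 6.3 gives neither the starting date nor whether holding one component counts.

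**4. Size for one subject.** Six months is about 26 weeks, so 26/2 = 13 backbone doses. A 2-week hold carried over to mFOLFIRINOX affects 1/13 = 7.7%; a 4-week hold, 2/13 = 15.4%. Removal from all treatment at week 8 forgoes about 13 − 4 = 9 of 13.

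**The case against.** No section says that mFOLFIRINOX continues; that side is an inference from silence. Section 5.3.1 goes on to holidays, weather and scheduling conflicts, and section 5.1 refers dose modifications to section 6, so 5.3.1 may well govern missed visits only. Section 11.6 does not say all study treatment, and a specific rule such as 6.1.1 could be taken to override a general one. Under the blind the rules apply to both arms, the analysis is ITT irrespective of compliance, and section 11.13 already tabulates withdrawals from treatment with reasons.

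Most of this stands, and it limits the point. It does not remove the explicit disagreements: three time limits, two end statuses, and a permanent stop against a hold and resume for the same event. For site instructions, silence on the backbone beside those rules is itself a defect.

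Two stronger readings are tempting.

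- **That the arms do not share the same background treatment.** The documents do not establish this. It needs more holds in Arm A and sites that extend them to the backbone, and no hold rate is given.
- **That the trial loses power.** Purely as an illustration, assume holds in 20% to 40% of Arm A and 5% to 10% of Arm B. Average backbone loss is then 0.20 × 7.7% = 1.5% to 0.40 × 15.4% = 6.2% in Arm A, and 0.05 × 7.7% = 0.4% to 0.10 × 15.4% = 1.5% in Arm B, a difference of about 1% to 5%. Power of 0.74 or 0.70 would need a true HR of 0.70 or 0.72, which removes 12% (1 − 0.357/0.405) or 19% (1 − 0.329/0.405) of the log-hazard-ratio effect. Nothing in the documents links the dose loss to such a change. Only frequent early removal from all treatment could be large, and no rate for it is given.

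**Conclusion.** The concern holds as an inconsistency in the instructions. For one related Grade 3 or higher event, the sections give different outcomes for ramucirumab/placebo, different limits (3 weeks of holding, 4 weeks of holding, 2 weeks after a second reduction) and different statuses. They leave the backbone unaddressed while only the blinded drug is held. Section 5.3.1 adds a possible delay of the whole cycle, is unclear for a missed Day 15 dose, and may be meant for scheduling misses only.

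For an affected subject, a carried-over hold of 2 to 4 weeks is 8% to 15% of the doses planned over 6 months. The average effect by arm cannot be estimated from the documents. More backbone loss in Arm A is plausible from the adverse-event lists but not shown. The logrank test remains a valid comparison of the assigned regimens. What is exposed is the interpretation of the result as an add-on effect to a common backbone. The point merits correction because the remedy is cheap, not because a bias has been demonstrated.

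**What to change.** Reconcile the synopsis with sections 5.3.1, 6.1 (including Table 4) to 6.1.6, 6.3 and 11.6. Each hold or stop of ramucirumab/placebo should carry one instruction for each component, one time limit and one status (off the drug, off study treatment or off the trial), identical in every section and in both arms. State whether 5.3.1 covers toxicity holds and how it applies to Day 15. State whether holding one component counts toward the 30-day limit, and from which date the days run. The clinical content is for the investigators to decide.

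Record on the eCRF which drug caused each delay, and report the dose intensity of each mFOLFIRINOX component by arm beside the PFS result. The cost is protocol wording, one eCRF field and one table; section 5.3.1 already asks for late infusions to be documented on the case report forms. Sample size and primary test need no change.
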